7. EVALUATION

Definition of variables

Sentinel lymph node: Defined as the first echelon lymph node where the tumor directly

flows through the lymphatic duct.

Isolated tumor cells: <0.2mm or less than 200 tumoral cells in a single histologic section

Micrometastases: 0.2mm-0.2cm or more than 200 tumoral cells in a single histologic

section.

Macrometastases: Metastases >0.2cm

Data to be abstracted:

Medical history and demographic data will be reviewed. Patients will be grouped in

group 1 (POLEmut), group 2 (MMRd), group 3 (NSMP), group 4 (p53abn), depending on

the molecular profile. Preoperative FIGO stage, modality of initial treatment, final

pathology diagnosis, preoperative pathology analysis, type of surgery, perioperative

details and adverse events will be reviewed. Follow up until the date will be reviewed as

well. (Appendix).

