4. OBJECTIVES

Primary objective

-To evaluate the lymph node involvement rate (sentinel) for each molecular subtype in patients with stage I/II EC.

Secondary objectives

- -To evaluate the lymph node involvement rate (sentinel and non-sentinel) for each prognostic risk group in patients with stage I/II EC.
- -To evaluate morbidity associated to SLN biopsy.
- -To assess compliance of ESGO quality Indicators.

We consider that our study will help to:

- ✓ Tailor the type of nodal staging depending on the molecular subgroup in early EC.
- ✓ Take a snapshot of the morbidity in SLN.
- ✓ Evaluate if the quality indicators described by ESGO are met.
- ✓ Know the degree of correlation between the molecular classification of the preoperative and the definitive biopsy.

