5. STUDY GENERAL DESIGN

STUDY GENERAL DESIGN

The study is a retrospective multicentric international observational study reviewing data of patients diagnosed with early-stage (FIGO stage I-II) EC and underwent surgical treatment with lymph node evaluation between January 2021 to December 2022, both included.

All data and records generated during this study will be kept confidential in accordance with Institutional policies and HIPAA on subject privacy. The Investigators and other site personnel will not use such data and records for any purpose other than conducting the study.

This protocol will be reviewed by the IRB of Clinica Universidad de Navarra, and the data collection will not start until the IRB approval is obtained. Each institution will be responsible of obtaining its own IRB/EC approval.

RECRUITMENT

A sample size of 1,032 patients may provide sufficient statistical power to evaluate the association between molecular subgroups and lymph node status. We assumed a 90% power for a 2-sided p-value of 0.05 and a minimum difference of 4.4 percentage points in prevalence rates of positive lymph nodes. We anticipated a potential dropout rate of 10%.

Gynaecological Cancer Centres/Units and hospitals regularly performing elective surgeries for EC internationally will be invited to participate in this study. Invitations will be sent through international/national and informal networks. Participating sites will register with the central audit team at Clinica Universidad de Navarra and will be provided with unique user access credentials for the database.

Each participating site (centre/unit/trust/hospital) will identify a principal investigator (PI) who will be responsible for coordinating data entry at their local site. The PI may have a bigger local reporting group/team with as many individuals as felt to be necessary to sustain the project. Team members may include gynaecological oncology trainees/fellows, medical/clinical oncologists, radiologists, pathologists, nurses, medical students, research staff, data managers. Each participating site will be provided a unique site code, individual username and password for database access. Inputting sites will only be able to access/see their own data and will not be able to see another site's data. The central coordinating centre team will be able to see individual data from all sites.

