Study IDs are unique to each patient and will be automatically assigned when a patient is registered onto the database. Study IDs will be assigned centrally by the REDCap bespoke database. Only one study ID should be created for each patient and new data registered on the appropriate electronic case record file (eCRF). Individual centres will retain access to their patient data and not provide identifiable information on the international database. Local sites will retain information on patient identifiable data (name, date of birth, address, telephone number) in a separate file but not share this with the central audit team. This information/file that links the study ID to the patient identifiers will be kept on the local centre/unit/hospital server, in case further clarification of data is required.

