6. STUDY POPULATION

INCLUSION CRITERIA

A patient will be considered eligible for inclusion in this study if all the following criteria are met:

- -Age 18 years or older
- -Patient was operated during 2021-2022
- -Histological confirmation of Endometrial Cancer with endometrioid histology or high risk histology (serous, clear cell, carcinosarcoma and mixed histologies)
- -Preoperative FIGO stage I or II by MRI or US
- -Preoperative CT-Scan or PET-CT without evidence of local or distant disease (could be omitted in low-risk and intermediate risk endometrial carcinoma with low grade histology)
- -Surgical protocol according to ESGO/ESTRO/ESP guidelines
- -A detailed sentinel lymph node study protocol must be accredited, either by ultrastaging or OSNA
- -Molecular analysis performed on the pathology specimen according to ESGO/ESTRO/ESP guidelines (POLE mutation analysis could be omitted in low-risk and intermediate risk endometrial carcinoma with low grade histology).

EXCLUSION CRITERIA

-Pregnant women

-Previous hysterectomy

-Previous pelvic/para-aortic lymphadenectomy

-Presence of extra-uterine disease (peritoneal, visceral or suspicious lymph node

metastasis)

-Past medical history of any invasive tumor

-History of previous abdominal or pelvic radiotherapy of any type (including

braquitherapy)

-History of preoperative neoadjuvant chemotherapy

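### Do the overlapping node-deposit definitions, and the silence on whether isolated tumour cells count, leave the primary involvement rate undefined?

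*Combined protocol and SAP*

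**What the plan says.** Section 7 (Evaluation), under Definition of variables, sets out three deposit classes. The smallest is given as "Isolated tumor cells: <0.2mm or less than 200 tumoral cells in a single histologic section". The middle class also offers size and count as alternatives, with the count again taken per section: "Micrometastases: 0.2mm-0.2cm or more than 200 tumoral cells in a single histologic". The largest class rests on size alone: "Macrometastases: Metastases >0.2cm".

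The primary objective in section 4 is "To evaluate the lymph node involvement rate (sentinel) for each molecular subtype in patients with stage I/II EC". The sample-size paragraph in section 5 uses a different term, assuming "a minimum difference of 4.4 percentage points in prevalence rates of positive lymph nodes". Neither term is tied to the section 7 classes, and section 8 names tests without defining the outcome.

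OSNA appears only as an eligibility condition in section 6 (and in the synopsis): "A detailed sentinel lymph node study protocol must be accredited, either by ultrastaging or OSNA". Section 7 points to an appendix for the data items. The readable appendix text holds only an operation guide and the title of Figure 2, an ultrastaging algorithm whose content is not shown.

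**The concern.** The primary result is a proportion, so its numerator needs a rule. Two things seem to be missing.

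First, the classes are not mutually exclusive as written. Size and cell count are joined by an either/or in both of the smaller classes, so a deposit whose two measures disagree satisfies two definitions, and no precedence is stated.

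Second, three classes are defined but nothing readable says which of them make a node involved. Two analysts could follow the text and report different rates, one with isolated tumour cells and one without, and the choice could be made after the data are seen. Sites using OSNA have no stated mapping to classes expressed in millimetres and cells per section. If sites entered only positive or negative, the call could also differ between sites.

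**Working it through.** **Inputs.** The class limits come from section 7, with 0.2 cm = 2 mm. The 1,032 patients and 10% dropout come from section 5. The 1,032 serves here only as a multiplier. It cannot be rebuilt from the stated inputs, because no baseline node-positive rate is given, and nothing below depends on how it was reached.

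**Step 1: the literal rule.** Let s be size in mm and c the cell count. Isolated tumour cells (ITC): s < 0.2 or c < 200. Micrometastasis: 0.2 ≤ s ≤ 2 or c > 200. Macrometastasis: s > 2.

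| s, c | Literal classes | Highest class met |
|---|---|---|
| 0.1, 50 | ITC | ITC |
| 0.15, 250 | ITC and micro | micro |
| 0.5, 150 | ITC and micro | micro |
| 0.5, 500 | micro | micro |
| 2.5, 150 | ITC and macro | macro |
| 3, 250 | micro and macro | macro |

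The overlap is real as a matter of logic. The last row shows that the literal reading cannot be intended: every deposit above 2 mm with more than 200 cells would be a micrometastasis as well as a macrometastasis.

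If only size is reported, the three size ranges (below 0.2, 0.2 to 2, above 2) give exactly one class. If only the count is reported, just the value 200 itself has no class. If both are reported, the highest class met is macro when s > 2, micro when 0.2 ≤ s ≤ 2 or when s < 0.2 with c > 200, and ITC when s < 0.2 with c ≤ 200. Those cells are exclusive and cover every case.

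**Step 2: when the overlap can reach the primary rate.** Three conditions must all hold: both measures were reported, they disagree at the ITC boundary, and ITC are not counted as involvement. The micro/macro overlap changes a label only.

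Shift in overall rate = (rate of any deposit) × (share of deposit-positive patients in conflict). Assumed ranges, neither given in the documents: 5–10% and 2–10%.

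- Low: 5% × 0.02 = 0.1 points; 0.001 × 1,032 = 1.0 patient
- High: 10% × 0.10 = 1.0 points; 0.010 × 1,032 = 10.3 patients
- With 10% lost (1,032 × 0.9 = 928.8): 0.9 to 9.3 patients
- If ITC count as involvement: 0

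**Step 3: the counting choice.** Shift = (rate of any deposit) × (share with ITC only). The ITC-only share is assumed at 20–50%.

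- 5% × 0.20 = 1.0 points; 10% × 0.20 = 2.0
- 5% × 0.50 = 2.5 points; 10% × 0.50 = 5.0
- In patients: 0.010 × 1,032 = 10.3 to 0.050 × 1,032 = 51.6

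These are shifts in the overall level. They should not be set against the 4.4-point design difference, which is a difference between groups. The effect on a subtype difference depends on how the ITC-only share varies by subtype, and the documents do not say.

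**Step 4: who would settle it.** The study is retrospective, on surgery from 2021–2022, and section 7 has final pathology abstracted from existing records. A report that already states a class does not need reclassifying. The classes are listed as variable definitions, which suggests (without proving) that class is recorded. Section 10 places the analysis with one central team. If class is recorded, a single cut, or rates with and without ITC, needs no new data. For unclear cases, section 5 has sites keep a local link to the patient "in case further clarification of data is required".

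**The case for a change.** The strongest case sets the overlap aside and rests on the numerator. Even if the either/or wording is only loose drafting, no readable section says which classes make a node involved. The study produces one headline rate per subtype, and that rate depends on the answer. A single central cut still needs a rule, preferably one chosen before the data are seen. Figure 2, judged by its title, concerns pathological processing and is not an obvious home for an endpoint definition or an OSNA code.

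Much of this stands as a description. The readable text contains no counting rule, and the choice could shift the overall rate by more than the overlap could. It does not establish a fault in the plan. The appendix list of data items cited in section 7 is exactly where field definitions and OSNA coding would be expected, and it is not among the readable material. Its absence here therefore cannot be held against the plan. The scenario in which sites enter only positive or negative has no textual support. No argument shows that either choice would distort the comparison between subtypes. Requiring new size and count fields would send sites in an unfunded study back to pathology reports, and deposits reported only by category would still keep the site's label.

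**Conclusion.** No change is needed. The overlap is loose drafting of three ordered classes, and any analyst would resolve it by taking the higher class. Its effect on the overall rate is zero if isolated tumour cells count. If they do not, it is 0.1 to 1.0 points under assumed deposit rates of 5–10% and conflict shares of 2–10%.

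Whether isolated tumour cells count is an unwritten detail worth 1.0 to 5.0 points of the overall rate, under the same deposit rates and assumed ITC-only shares of 20–50%. With classes defined separately and analysed centrally, it can be handled by stating the choice and showing the subtype rates both ways. OSNA coding remains an open question and not a demonstrated defect.

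This conclusion assumes that deposit class is recorded, as its place among the defined variables suggests. It would weaken if the data-item list showed that sites enter only positive or negative. None of the ranges measures site disagreement, OSNA coding or bias in the subtype difference, and the documents give no figure that would allow it.

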8. STATISTICAL ANALYSIS

Quantitative data will be presented as mean and standard deviation and qualitative

variables with absolute values and percentages. Additionally, qualitative variables

among groups will be compared by chi-square test or Fisher exact test; and quantitative

variables with t-test and ANOVA test. For the multivariate analysis a logistic regression model will be used.

Survival analysis will be performed using the Kaplan-Meier method and log-rank tests. Alpha error will be set at 5%.

9. ETHICAL, LEGISLATIVE AND REGULATORY CONSIDERATIONS

Ethical considerations

The investigator will ensure that this study is conducted in full conformance with the principles of the "Declaration of Helsinki" or with the laws and regulations of the country in which the research is conducted, whichever affords the greater protection to the individual. All data will be collected on a customised, secure, password protected central REDCap database hosted by Clinica Unviersidad de Navarra. REDCap is used internationally to securely collect research data. All collected data will be transmitted and held anonymously.

Investigator responsibilities

The principal investigator of each site must conduct the study in accordance with the research protocol and with current regulations.

The investigator should not implement any deviation from, or changes of the protocol without authorized in writing by the principal investigator and without the previous authorization of the Ethics Committee and competent authorities of proposed changes. The principal investigators are responsible of respecting the study confidentiality.

Confidentiality of study documents and patient records

The investigator must ensure that patients' anonymity will be maintained and that their identities are protected from unauthorised parties. On CRFs or other documents submitted to the principal investigator, patients should not be identified by their names, but by an identification code.

Funding and conflict of interest

This study has not received funding from any public or private for-profit entity, nor will it admit any during the development of the study. None of the investigators or patients will receive any financial or material compensation for the development of the study, nor do they have any financial conflict of interest in the conduct of the study.

10. PUBLICATIONS

We are currently in the design and approval phase of the study and expect to complete this phase by the end of 2022.

Between January and February 2023 we will start the phase of dissemination of the project and recruitment of institutions wishing to participate in it, once the total number of participating centres is obtained, we will start recruiting between March and May 2023. Throughout this process, several virtual meetings will be held to inform the heads of each institution of the status of the project as well as to resolve any doubts that may arise. In the same way, several reminder e-mails will be sent to ensure that the recruitment process is carried out on time.

Once recruitment has been completed, we will proceed to the analysis of the data by our statistical team and the research committee. Preliminary results are intended to be presented at the ESGO Congress in ISTANBUL in October 2023.

It will be the responsibility of the Principal Investigator to obtain and publish the results of this study in high impact journals indexed in the Journal Citation Report (Pubmed). The tentative deadlines for publication of the main results will be December 2023.

With respect to authorship in the different papers, the following rules will be followed, the acceptance of which is considered implicit to participation in this study. We will always try to include the maximum number of authors, as well as the maximum number of participating centers, even those with the lowest participation, as follows:

- The number of authors per publication will be a maximum of 20 authors (unless the journal is flexible, in which case the maximum allowed will be included). The general order of authors will be established by individual order of inclusion of cases in the study. If any author considers that another researcher from his/her institution should participate as a co-author in his/her place, this will be communicated in time for inclusion in the corresponding publication.
- In case the limitation of authors makes it necessary to reduce the number of authorships, it will be reduced following the same rule of inclusion of cases in the study.
- There will be 4 fixed positions in the publications corresponding to the persons in charge of the writing and elaboration of the articles (first and second author), coordination and development of the study (last author PI), statistical study and methodology (penultimate author).
- -For the rest of the positions, half will correspond to the authors with the highest number of cases introduced in all the publications derived; and the other half consecutively to the authors of the institutions that follow them in number of cases.

 For example, in the case of 32 collaborating researchers arranged in order of participation and 3 articles to be written, the order of authorship would be:
 - Article 1: 4 fixed positions + authors centers of 1--8 + Authors 9-16
 - Article 2: 4 fixed positions + authors centers of 1--8 + Authors 17-24
 - Article 3: 4 fixed positions + authors centers of 1--8 + Authors 25-32

In this way, the inclusion of the maximum and most varied number of authors will be encouraged while giving priority to the greatest participation and work of the study's collaborators.

-At the end of the list of authors of each publication, "on behalf of SENECA group collaborative" will be written. Authors who cannot be included as such in each publication will be included as collaborators or in the acknowledgements according to the possibilities of each journal.

Uterine manipulator	If being used, insert uterine manipulator after tracer injection	Mandatory
White light inspection	Prior to SLN mapping, conduct an inspection of the pelvic areas	Mandatory
Round ligament & Infundibulopsivic ligament	Preserve	Optional
	Divide	Optional
External vessels	Identify the external illac vessels	Mandatory
internal iliac artery	Identify the internal iliac artery	Mandatory
Ureter	Identify the ureter	Mandatory
Obliterated umbilical ligament	Identify the obliterated umbilical ligament	Mandatory
Uterine artery	Identify the uterine artery (medial to the ureter)	Optional
Paravesical space	Open the paravesical space	Mandatory
Direction of dissection	Start sentinel lymph node mapping at the level of the uterine artery and continue dissection LATERALLY away from the uterus	Mandatory
	Start sentinel lymph node mapping at the level of the uterine artery and and continue MEDIALLY toward the uterus	Optional
	Start sentinel lymph node mapping at the level of the uterine artery and and continue toward the pre-sacral area.	Optional
	Start sentinel lymph node mapping at the most highlighted node and dissect proximally (TOWARD cervis)	Optional
	Start sentinel lymph node mapping at the most highlighted node and dissect cephalad (AWAY from carrix)	Optional
Dissection technique	Use blant or electrosurgical technique Assold disrupting lymphatic channels during dissection Ensure isolation of node from local snatorny	Mandatory Mandatory Mandatory
Definition of the sentinel node	A sentinel node is defined as The most proximal node is the most proximal node is defined as the node classet to the under regardless of broaden), invespective of the node station in which the node is found A single manufact node or a single node plus its next station echelon node(s).	Mandatory Mandatory
SLN dissection	A single mapper node or a single node plus its next station echeion node; SLN dissection should be completed in one hemi-pelvis before proceeding to the	Mandatory
DELT GENERALISM	contralateral side	internation,
Troubleshooting	Tracibish drolling when no nodes are respirity includes any one, or confessation of, the following option: • Wat, undestable adsection on the contralations' side bather extensing to original side between the standing or original side between the contralations of the contralations	Mandatory
Specimen extraction	Removal of nodes without using a containment device	Prohibited
Proof of sentinel node	Use ex-vivo green fluorescence to prove the sentinel node	Mandatory
Specimen labeling	Label specimens according to laterality (right/left) AND nodal station (obturator/external iliac/internal iliac/presscral/common iliac/sortic/canal)	Mandatory
Ultrastaging	Use enhanced pathology techniques, such as immunohistochemistry, for ultrastaging of sentinel nodes	Mandatory
Final consensus on mandatory a ICG, indocyanine green.	nd prohibited steps of sentinel lymph node dissection (SLND) by minimally invasive surgery in e	ndometrial cancer.

Figure 1 Operation guide

[figure not shown]

Figure 2 Memorial Sloan-Kettering Cancer Center's Pathologic Ultrastaging Algorithm for Sentinel Lymph Nodes
